e pourcentage. Si li comme référence po l'évaluer. Vous poi nouvements dyskine nouvements dyskine louloureuse du matir la cours de la sen juotidienne, en incl veillé(e) heures. Du nouvements accadi remblements, qui es louloureuses au pie parler plus tard. Co accadiques ou avec esquelles ceux-ci su 0 = normal 1 = minime 2 = léger 3 = modéré	e patient a des dyskinesies dur ur vous assurer que les patients uvez aussi utiliser vos propres d étiques que vous avez vu préc étiques types vus sur d'autres n et de la nuit. maine précédente, combien d'he uant le sommeil nocturne et rant ces heures d'éveil, combien fiques ou avec secousses ? N t une secousse régulière d'arrière d ou des spasmes tôt le matin, oncentrez-vous seulement sur c secousses. Additionnez toutes rviennent habituellement. Combie : pas de dyskinésies. : < 25% du temps éveillé dans : de 26% à 50% du temps éveillé dans	et les aidants comprennent ce qu'ils sont en train compétences d'interprétation pour représenter les tédemment chez le patient, ou leur montrer des patients. Excluez de cette question la dystonie la sieste diume ? D'accord, si vous dormez heures, vous êtes d'heures au total avez-vous de dandinement, de le comptez pas les périodes où vous avez des e en avant, ou les périodes vous avez des crampes ou pendant la nuit. Je vous demanderai de m'en ces types de dandinement, la journée durant en d'heures (utilisez ce nombre pour votre calcul).
e pourcentage. Si l comme référence po l'évaluer. Vous pou- nouvements dyskine nouvements dyskine louloureuse du matir lau cours de la sen- juotidienne, en incl veillé(e) heures. Du nouvements saccadi veillé(e) heures. Du nouvements saccadi leuloureuses au pie- saccadiques ou avec esquelles ceux-ci su 0 = normal 1 = minime 2 = léger 3 = modéré 4 = sévère	e patient a des dyskinesies dur ur vous assurer que les patients uvez aussi utiliser vos propres d étiques que vous avez vu préc étiques types vus sur d'autres n et de la nuit. naine précédente, combien d'he uant le sommeil nocturne et rant ces heures d'éveil, combien liques ou avec secousses ? N t une secousse régulière d'arrière d ou des spasmes tôt le matin, oncentrez-vous seulement sur c secousses. Additionnez toutes rviennent habituellement. Combie : pas de dyskinésies. : < 25% du temps éveillé dans : de 26% à 50% du temps éveil : > 75% du temps éveillé dans	ant la consultation, vois pouvez les fui signale et les aidants comprennent ce qu'ils sont en train compétences d'interprétation pour représenter les rédemment chez le patient, ou leur montrer des patients. Excluez de cette question la dystonie eures dormez-vous habituellement sur une base la sieste diurne ? D'accord, si vous dormez heures, vous étes d'heures au total avez-vous de dandinement, de le comptez pas les périodes où vous avez des e en avant, ou les périodes vous avez des crampes ou pendant la nuit. Je vous demanderai de m'en ces types de dandinement, de mouvements les heures éveillées pendant la journée durant en d'heures (utilisez ce nombre pour votre calcul).
e pourcentage. Si li comme référence po l'évaluer. Vous pou nouvements dyskine nouvements dyskine louloureuse du matir Au cours de la sen quotidienne, en incl eveillé(e) heures. Du nouvements saccac remblements, qui es touloureuses au pie barler plus tard. Ca accadiques ou avec esquelles ceux-ci su 0 = normal 1 = minime 2 = léger 3 = modéré 4 = sévère	e patient a des dyskinesies dur ur vous assurer que les patients uvez aussi utiliser vos propres d étiques que vous avez vu préc étiques types vus sur d'autres n et de la nuit. naine précédente, combien d'he uant le sommeil nocturne et rant ces heures d'éveil, combien tiques ou avec secousses ? N t une secousse régulière d'arrière d ou des spasmes tôt le matin, procentrez-vous seulement sur c secousses. Additionnez toutes rviennent habituellement. Combie : pas de dyskinésies. : <25% du temps éveillé dans : de 26% à 50% du temps éveil : >75% du temps éveillé dans	et les aidants comprennent ce qu'ils sont en train compétences d'interprétation pour représenter les tédemment chez le patient, ou leur montrer des patients. Excluez de cette question la dystonie eures dormez-vous habituellement sur une base la sieste diurne ? D'accord, si vous dormez heures, vous êtes d'heures au total avez-vous de dandinement, de le comptez pas les périodes où vous avez des e en avant, ou les périodes vous avez des crampes ou pendant la nuit. Je vous demanderai de m'en ces types de dandinement, de mouvements les heures éveillées pendant la journée durant en d'heures (utilisez ce nombre pour votre calcul).
e pourcentage. Si I comme référence po l'évaluer. Vous poi nouvements dyskim louloureuse du matir Au cours de la sen quotidienne, en incl éveillé(e) heures. Du nouvements saccad remblements, qui es parler plus tard. Cé accadiques ou avec esquelles ceux-ci su 0 = normal 1 = minime 2 = léger 3 = modéré 4 = sévère	 e patient a des dyskinesies dur ur vous assurer que les patients uvez aussi utiliser vos propres d étiques que vous avez vu préc étiques types vus sur d'autres n et de la nuit. maine précédente, combien d'he uant le sommeil nocturne et rant ces heures d'éveil, combien liques ou avec secousses ? N t une secousse régulière d'arrière d ou des spasmes tôt le matin, oncentrez-vous seulement sur c secousses. Additionnez toutes rviennent habituellement. Combie : pas de dyskinésies. < 25% du temps éveillé dans : de 26% à 50% du temps éveil : > 75% du temps éveillé dans 	ant la consultation, vois pouvez les fui signale et les aidants comprennent ce qu'ils sont en train compétences d'interprétation pour représenter les tédemment chez le patient, ou leur montrer des patients. Excluez de cette question la dystonie eures dormez-vous habituellement sur une base la sieste diurne ? D'accord, si vous dormez heures, vous étes d'heures au total avez-vous de dandinement, de le comptez pas les périodes où vous avez des e en avant, ou les périodes vous avez des crampes ou pendant la nuit. Je vous demanderai de m'en ces types de dandinement, de mouvements les heures éveillées pendant la journée durant en d'heures (utilisez ce nombre pour votre calcul).
e pourcentage. Si I comme référence po d'évaluer. Vous poi nouvements dyskin nouvements dyskin houloureuse du matir Au cours de la sen puotidienne, en incl veillé(e) heures. Du nouvements saccad termblements, qui es fouloureuses au pie parler plus tard. Co accadiques ou avec esquelles ceux-ci su 0 = normal 1 = minime 2 = léger 3 = modéré 4 = sévère	 e patient a des dyskinesies dur ur vous assurer que les patients uvez aussi utiliser vos propres de étiques que vous avez vu préc étiques types vus sur d'autres n et de la nuit. naine précédente, combien d'he uant le sommeil nocturne et rant ces heures d'éveil, combien liques ou avec secousses ? N t une secousse régulière d'arrière d ou des spasmes tôt le matin, concentrez-vous seulement sur c secousses. Additionnez toutes rviennent habituellement. Combie : pas de dyskinésies. < 25% du temps éveillé dans : de 26% à 50% du temps éveil : > 75% du temps éveillé dans 	ant la consultation, vois pouvez les fui signale et les aidants comprennent ce qu'ils sont en train compétences d'interprétation pour représenter les tédemment chez le patient, ou leur montrer des patients. Excluez de cette question la dystonie eures dormez-vous habituellement sur une base la sieste diume ? D'accord, si vous dormez heures, vous êtes d'heures au total avez-vous de dandinement, de le comptez pas les périodes où vous avez des e en avant, ou les périodes vous avez des crampes ou pendant la nuit. Je vous demanderai de m'en ces types de dandinement, de mouvements les heures éveillées pendant la journée durant en d'heures (utilisez ce nombre pour votre calcul).

4.	2	Retentisse	emer	nt fonctionnel des dyskinésies _				
Déterminez le degré de retentissement que les dyskinésies ont sur la fonction quotidienne du patient en termes d'activités et d'interactions sociales. Utilisez la réponse du patient et de l'aidant à vos questions et vos propres observations pendant la visite en consultation pour arriver à la meilleure réponse. Au cours de la semaine précédente, avez-vous eu des problèmes en faisant des choses ou en étant avec des gens lorsque ces mouvements saccadés apparaissaient ?vous ont-ils empêché de faire des choses ou d'être avec des gens ?								
0	=	normal	:	pas de dyskinésies ou pas de retentissement des dyskinésies sur les activités et les interactions sociales				
1	=	minime	:	les dyskinésies retentissent sur quelques activités, mais le patient effectue habituellement toutes les activités et participe à toutes les interactions de la vie sociale pendant les périodes dyskinétiques.				
2	=	léger	:	les dyskinésies retentissent sur beaucoup d'activités, mais le patient effectue habituellement toutes les activités et participe à toutes les interactions de la vie sociale pendant les périodes dyskinétiques.				
3	=	modéré	:	les dyskinésies retentissent sur les activités, au point que le patient ne peut effectuer certaines activités et ou ne peut pas participer à certaines activités sociales pendant les épisodes dyskinétiques.				
4	=	sévère	:	les dyskinésies retentissent sur la fonction au point que le patient ne peut effectuer la plupart des activités et ou participer à la plupart des interactions sociales pendant les épisodes dyskinétiques.				
B.	B. FLUCTUATIONS MOTRICES							
4.	3	Durée des	péri	iodes ON _				
Utili	sez F. C	le nombre alculez le p	d'heu ource	ures éveillées provenant de 4.1 et déterminez les heures passées en condition entage. Si le patient a un épisode OFF durant la consultation, vous pouvez vous				

appuyer sur cet état comme référence. Vous pouvez aussi utiliser votre connaissance du patient pour décrire une période OFF typique. De plus, vous pouvez aussi utiliser vos propres compétences d'interprétation pour représenter une période OFF déjà vue auparavant chez le patient, ou leur montrer la fonction OFF typique d'autres patients. Notez le nombre type d'heures OFF, car vous aurez besoin de ce nombre pour compléter le 4.6.

Certains patients atteints de la maladie de Parkinson retirent un bon effet de leurs médications pendant les heures éveillées et nous appelons cela la période ON. D'autres patients prennent leurs médications mais ont encore quelques heures de baisse de régime, de période mauvaise, ralentie ou période de tremblement. Les médecins appellent ces mauvaises périodes, période OFF. Au cours de la semaine précédente, vous m'avez dit auparavant que vous êtes généralement éveilléheures par jour. Durant ces heures éveillées, combien d'heures au total avez-vous habituellement ce type de baisse régime ou épisode OFF (utilisez ce nombre pour vos calculs).

0 = norm	al :	pas de période OFF.
----------	------	---------------------

- 1
 = minime
 :
 >25% du temps éveillé dans la journée.

 2
 = léger
 <td:	:
 de 26% à 50% du temps éveillé dans la journée.

 3
 = modéré
 :
 de 51% à 75% du temps éveillé dans la journée.

 4
 = sévère
 :
 >75% du temps éveillé dans la journée.

1 - total des heures éveillées ______ 2 - total des heures OFF ______

3 - % OFF = ((2/1) x100)

4.4	Re	etentisseme	ent	fonctionnel des fluctuations _
Déter	mine	ez le degré	de	retentissement que les fluctuations motrices ont sur le fonctionnement
quotio	dien	du patient e	n te	rmes d'activités et d'interactions sociales. Cette question se concentre sur la
differe	ence	entre l'état	ON 0	et l'état OFF. Si le patient n'a pas de période OFF, l'évaluation doit être 0, mais
si les	pat	ients ont de t	tres	legeres fluctuations, il est encore possible de coter u sur cet item s'il n'y a pas
de ret	tentis	ssement sur	leurs	s activites. Utilisez la reponse du patient et de l'aldant a votre question et votre
Propri	e op	servation per	ndan	it la visite en consultation pour arriver a la meilleure reponse.
como	ine	précédente	Ave	ril ces baisses de regime ou pendues OFF sont survenues au cours de la
dene	nor	precedenie. repport ou re	AVC cto	de la journée lorsque vous sentez que vos médicaments marchent bien 2 V s
t-il ce	par i vrtain	es choses o	ue i	vous faites habituellement nendant une honne nériode, qui vous nosent des
proble	ème	s ou que vou	s an	rêtez de faire pendant une période de baisse de régime ?
p				ele la la pendan une penede de salece de regime .
0	=	normal	2	pas de fluctuation ou pas de retentissement des fluctuations sur l'accomplissement
				des
1	=	minime	2	les fluctuations retentissent sur quelques activités, mais pendant la période OFF, le
				patient accomplit habituellement toutes les activités et participe à toutes les
				interactions sociales qui surviennent typiquement pendant la période ON.
2	=	léger	2	les fluctuations retentissent sur beaucoup d'activités, mais pendant la période OFF,
				le patient le accomplit encore habituellement toutes les activités et participe à toutes
				les interactions sociales qui surviennent typiquement pendant la période ON.
3	=	modéré	2	les fluctuations retentissent sur la réalisation des activités pendant la période OFF au
				point que le patient n'accomplit habituellement pas certaines activités et ou ne
				participe pas à certaines interactions sociales qui sont effectuées durant les périodes
				ON
4	=	sévère	2	les fluctuations retentissent sur le fonctionnement au point que durant la période OFF
				le patient n'accomplit pas la plupart des activités, ni ne participe à la plupart des
				interactions sociales qui sont effectuées pendant les périodes ON.

4.5 Complexité des fluctuations

Déterminez la prévisibilité habituelle des épisodes OFF, qu'ils soient dus à la dose, au moment de la journée, à la prise de nourriture ou à d'autres facteurs. Utilisez l'information fournie par le patient et les aidants et complétez avec vos propres observations. Vous demanderez si le patient peut s'attendre à ce qu'elles arrivent toujours à une période précise, survenant la plupart du temps à un moment particulier (dans ce cas- là, vous évaluerez d'avantage pour séparer minime de léger), ou à ce qu'elles arrivent quelquefois à un moment précis ou si elles sont totalement imprévisibles ? En réduisant le pourcentage, vous obtiendrez la réponse correcte.

Pour certains patients, les périodes mauvaises ou OFF arrivent à certains moments de la journée ou quand ils sont engagés dans des activités comme manger ou faire de l'exercice. Au cours de la semaine précédente, savez-vous habituellement quand vos périodes mauvaises vont survenir ? En d'autres mots, est-ce que vos baisses de régime apparaissent toujours à un moment donné ? Apparaissent-elles le plus souvent à un moment donné ? Apparaissent-elles seulement quelquefois à un moment donné ? Vos baisses de régime sont-elles totalement imprévisibles ?

0	=	normal	:	pas	de	fluctuation	motrice
_							

- 1 = minime : les périodes OFF sont prévisibles tout ou presque tout le temps (> 75%).
- 2 = léger : les périodes OFF sont prévisibles la plupart du temps (51-75%).
- 3 = modéré : les périodes OFF sont prévisibles quelquefois (26-50%).
- 4 = sévère : les périodes OFF sont rarement prévisibles (<25%).

C. DYSTONIE ON

4.6 Dys	tonie doul	oureuse en état ON	_	
Pour les épisodes O nombre d' associées à Dans une d'heures d contrôlée. F spasmes d moments de ferait-il ?	patients q FF comprer heures en une dyston question de période Pendant ces louloureux e la journée	ui ont des fluctuations motrices, nent habituellement une dystonie d période OFF (4.3). Parmi ces hei ie et calculez le pourcentage. S'il n'y que je vous ai posé(e)préc mauvaise ou de temps « OFF » périodes mauvaises ou OFF, ave. ? Sur un total de heures de ce durant lesquels ces crampes doulo	déterminez dans quelle proportion des douloureuse? Vous avez déjà déterminé le ures, déterminez combien d'entre-elles sont y a pas de période OFF, notez 0. cédemment, vous dites avoir généralement quand votre maladie de Parkinson est mal z-vous habituellement des crampes ou des tte période mauvaise, si vous ajoutez tous les pureuses apparaissent, combien d'heures cela	
0 = nor 1 = mir 2 = lég 3 = mo 4 = sév	mal : nime : er : déré : vère :	pas de dystonie ou pas de période < 25% du temps en état OFF. de 26% à 50% du temps en état O de 51% à 75% du temps en état O > 75% du temps en état OFF.	OFF. IFF. IFF.	
			1 - total des heures OFF	

2 - total des heures OFF avec dystonie _____ 3 - % de dystonie OFF = ((2/1) x100) _____

14.14 Appendix N – Hoehn and Yahr stage

A compléter lors du screening et Visite 4.

STADE HOEHN & YAHR

- □ Stade 0 : pas de signe de la maladie.
- □ Stade 1 : maladie unilatérale.
- **Stade 1,5 :** maladie unilatérale, plus atteinte axiale.
- □ Stade 2 : maladie bilatérale sans trouble de l'équilibre.
- □ Stade 2,5 : maladie bilatérale légère avec rétablissement lors du test de la poussée.
- Stade 3 : maladie bilatérale légère à modérée : une certaine instabilité posturale, physiquement autonome.
- Stade 4 : handicap sévère : toujours capable de marcher ou de se tenir debout sans aide.
- □ Stade 5 : malade en chaise roulante ou alité sauf s'il est aidé.

14.15 Appendix O – Freezing of gait questionnaire.

A compléter à chaque visite : Baseline, Visite 3, et Visite 4.

Evaluation Freezing – Kinésithérapie

Date. Visite.	ID Patient :	Date:		Visite :	
---------------	--------------	-------	--	----------	--

Instructions pour l'administrateur :

Veuillez administrer le questionnaire suivant au patient, en notant sa réponse à chaque question posée avec le numéro correspondant. Le questionnaire doit être réalisé lorsque le patient est en condition "on". Les réponses doivent refléter l'expérience du patient au cours de la dernière semaine.

1. Lorsque vous êtes au plus mal, vous marchez :

- 0 Normalement
- 1 presque normalement parfois lentement
- 2 Lentement mais toujours sans aide
- 3 Avec une personne ou une aide technique
- 4 Marche impossible

2. Vos difficultés de marche affectent-elles vos activités quotidiennes ou votre indépendance ?

- 0 Pas du tout
- 1 Peu
- 2 Modérément
- 3 Enormément
- 4 Marche impossible

3. Ressentez-vous vos pieds « collés » au sol lors de la marche, lors des demi-tours ou lors de l'initiation de la marche ?

- 0 Jamais
- 1 Très rarement une fois par mois
- 2 Rarement une fois par semaine
- 3 Souvent au moins une fois par jour
- 4 Toujours a chaque fois que vous marchez

4. Quelle durée peuvent avoir vos épisodes de Freezing ?

- 0 Jamais arrivé 1 1 2 s
- 11 2323 - 10s
- 311 30 s
- 4 Impossible de marcher plus de 30 s

5. Quelle est la durée de votre épisode de freezing lors de l'initiation du premier pas ?

- 0 Aucune
- 1 Environ 1 s pour initier le pas
- 2 Environ 3 s pour initier le pas
- 3 Environ 10 s pour initier le pas
- 4 Environ 30 s pour initier le pas

6. Quelle est la durée de votre épisode de freezing lors des demi-tours?

- 0 Aucune
- 1 Demi-tour en 1 2 s
- 2 Demi-tour en 3 10 s
- 3 Demi-tour en 11 30 s

CIP Number 2023-A00150-45 Final version 0.2

4 Demi-tour en + de 30 s ou impossible

14.16 Appendix P – PDSS 2

A remplir à chaque visite : Baseline, Visite 1, Visite 2, Visite 3 et Visite 1.2, Visite 2.2, Visite 4 si applicable.

Questionnaire sur le sommeil Maladie de Parkinson (PDSS)

Comment mesureriez-vous les éléments suivants d'après ce que vous avez vécu au cours des 7 derniers jours ? (Mettez une croix sur la ligne de la page de droite, à l'endroit correspondant à votre situation)

- 1. Globalement, la nuit, la qualité de votre sommeil a été :
- 2. Avez-vous eu des difficultés à vous endormir le soir ?
- 3. Avez-vous eu des difficultés à rester endormi(e) ?
- 4. La nuit ou le soir, avez-vous ressenti une agitation dans les jambes ou les bras qui vous a géné(e) pour dormir ?
- 5. Lorsque vous étiez dans votre lit, vous êtes-vous agité(e) la nuit ?
- 6. Avez-vous fait des rêves pénibles la nuit ?
- 7. La nuit, avez-vous eu des hallucinations pénibles (vous avez vu ou entendu quelque chose qui, en réalité, n'existe pas) ?
- 8. Vous êtes-vous levé(e) la nuit pour uriner ?
- 9. Avez-vous eu des pertes d'urine parce que vous étiez incapable de bouger à cause d'un blocage (état de quasi-immobilité parce que vos médicaments ne font plus d'effet) ?
- 10. Vous êtes-vous réveillé(e) la nuit parce que vous aviez des fourmillements ou une sensation d'engourdissement dans les bras ou les jambes ?
- 11. La nuit, avez-vous eu des crampes douloureuses dans les bras ou les jambes durant votre sommeil ?
- 12. Vous êtes-vous réveillé(e) tôt le matin avec des douleurs dans les bras ou les jambes dues à une mauvaise position ?
- 13. Lorsque vous vous êtes réveillé(e) le matin ou au cours de la nuit, avez-vous eu des tremblements ?
- A votre réveil ou pendant la matinée, vous êtes-vous senti(e) fatigué(e) ou avez-vous eu envie de dormir ?
- 15. Vous est-il arrivé de vous endormir subitement pendant la journée ?

Numéro de / ID Patient:

Date de l'évaluation://	
ECHELLE VISUELLE ANALOGIQUE pour PDSS	

	humu	Hudini	minut	H H H H H	milim	hinifini	milim	hindini	HIN	
1.		2	3	4	Б	6	'	0	9	10
	TRES MAU	VAISE							DICEL	ENTE
	0 1	2	3	4	5	6	7	8	9	10
2.	TOWOURS								, JA	MAIS
_	ļuuluuļu	uluuluul	unfunt		minn	HIII	huiluu	hulun	HIII	HHH
з.	Ļ	2	3	4	5	6	'	•	9	10
	TOUJOURS						milion		JA HHHHHH	MAIS
	0 1	2	3	4	5	6	7	8	9	10
4.	TOWOURS								, JA	MAIS
_	ļuuluuļu	n Inn Juni	unliunt	mim	mim	HIII	minu	hulun	HIII	HHH
5.		2	3	4	5	ь		8	9	10
	TOWOURS								AL HHHHHH	MAIS
~	0 1	2	3	4	5	6	7	8	9	10
6.	TOWOURS								, JA	MAIS
_	ļuuturļu	mminn	mim	mim	milun	HIII	minn	HII	HIII	HHH
7.	0 1	2	3	4	5	ь		8	9	10
	TOWOURS								JA IIIIIIIII	MAIS
~	0 1	2	3	4	5	6	7	8	9	10
8.	TOWOURS								, JA	MAIS
	ļuutuuļu	uuu juu	unium	nu[mu	HIII	HIII	minn	hini	HIII	
9.		2	3	4	5	ь		8	9	10
	TOWOURS						mulmu		AL HHHHHH	MAIS
10	0 1	2	3	4	5	6	7	8	9	10
10.	TOWOURS								, JA	MAIS
	ļiiiiiiii		HII	HII IIIII	milium	HIII	milmi	HIII	HIII	
11.	 	2	3	4	5	6	'	0	9	- 10
	TOWOURS								ar IIIIIIII	MAIS
10	0 1	2	3	4	5	6	7	8	9	10
12.	TOWOURS								, JA	MAIS
_		mminn	HII	H H H H H H	milium	hiiliii	huilinn	Innfinn	HIII	10
13.			3	4	5	6	'	0		
	TOUJOURS			l					at IIIIII	MAIS
14	0 1	2	3	4	5	6	7	8	9	10
14.	TOWOURS								JA	MAIS
			HILLIN		HILI				HIII	10
15.		2	3	4	3	3		3		
	FREQUEM	MENI							JA	MAIS

14.17 Appendix Q – Patient global impression of severity (PGI-S) and improvement (PGI-I)

14.17.1 PGI-S : patient global impression of severity

A compléter à la visite Baseline

Veuillez mettre une croix en face de la réponse qui décrit le mieux votre état de santé actuel :

- o Pas de symptôme
- Très peu de symptômes
- Peu de symptôme
- Symptômes modérés
- o Symptômes légèrement sévères
- o Symptômes sévères
- Symptômes très sévères

14.17.2 PGI-I : patient global impression of improvement

A compléter à Visite 3 et Visite 4 si applicable.

Veuillez mettre une croix en face de la réponse qui décrit le mieux l'évolution de votre état de santé depuis votre dernière visite :

- Beaucoup mieux
- Mieux
- Pas de changement
- Un peu moins bien
- \circ Moins bien
- Beaucoup moins bien

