	During their routinely scheduled visit at the investigational site patients who express interest in participating in the study will be introduced to the device. If judged to be comfortable with and interested in the technology, patients will return to their home to consider their participation. There is a reflexion period that lasts at least fifteen days up to one month If the patient decides to participate in the study, they return to the site for the screening visit. Once the informed consent is signed the screening assessments will be performed by the investigator (the neurologist). If eligible, the patients will be randomised either into the conventional physiotherapy (CPt control group) or the FeetMe rehabilitation program (experimental group).
	Primary Intervention Period
	Once randomised patients will proceed to the Baseline Visit (BL). At the BL visit, all participants (experimental and CPt control group) will be trained to use the FeetMe devices and will wear the insoles as much as possible throughout the visit. Standard gait and balance assessments will be performed (6 minute walk test (6MWT), MiniBESTest). Additionally, patients will perform multiple clinical assessments designed to assess: disease severity, gait, balance, mobility, etc. by completing different surveys.
	Following the BL visit, all patients will enter an initial 12 week period according to their patient group. Every patient in the study will be provided with a pair of insoles and will take the device to their homes. All patients, whatever the group of randomisation, will be asked to wear them as much as possible for 14 days after the BL visit to allow continuous gait data collection. This will permit the gathering of extensive data on a considerable number of gait parameters in a more familiar and natural setting reflecting real-life conditions. The FeetMe

patients will then continue to use the insoles according to the FeetMe rehabilitation program schedule.						
During the Primary Intervention Period (PIP), all patients will participate in two remote visits: Visit 1 (four weeks after BL) and Visit 2 (eight weeks after BL). During these visits, all patients will perform a short battery of self-reported questionnaires.						

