	Change from baseline to Week 12 (Visit 3) in Stance Time Variability assessed during the 6MWT.
	Secondary Endpoints
	• Rate of falls at Week 12 based on the results of the falls diary.
	• Change from baseline to Week 12 (Visit 3) in the asymmetry of the swing duration assessed during the 6MWT.
	• Change from baseline to Week 12 (Visit 3) in the Mini-BESTest.
	• Change from baseline to Week 12 (Visit 3) in Unified Parkinson's Disease Rating Scale (MDS-UPDRS) Part III sub-score.
	• Change from baseline to Week 12 (Visit 3) in the results of the Parkinson Disease Questionnaire (PDQ-39).
	Exploratory Endpoints
	• Rate of falls at Week 24 based on the results of the falls diary.
	• Change from Baseline to Week 24 (Visit 4) and from Week 12 (Visit 3) to Week 24 in:
	- Gait velocity (cm/s) assessed during the 6MWT
	- Stance Time Variability assessed during the 6MWT
	- Asymmetry of the swing duration assessed during 6MWT
	- the Mini-BESTest
	- MDS-UPDRS Part III sub-score
	- the results of the PDQ-39
	 Change from Baseline to Week 12 (Visit 3) and to Week 24 (Visit 4) and from Week 12 to Week 24 in the:
	- gait parameters measured by the FeetMe Monitor during the 6MWTs other than ones of the primary and secondary endpoints
	- gait parameters measured by the FeetMe Monitor during remote gait monitoring
	- results of the pain VAS
	- results of the Parkinson Disease Sleep Scale 2 (PDSS2)
	- results of the Clinical and Patient Global Impression of Severity scales (CGI/PGI-S)
	- results of the Clinical and Patient Global Impression of Improvement scales (CGI/PGI-I)
	• results of the MDS-UPDRS I, II and IV sub scores
	• Actual versus prescribed time spent on physiotherapy at Week 12 and Week 24.
· · · · · · · · · · · · · · · · · · ·	

	• Results of the Patient and Investigator satisfaction questionnaire.
	• Number of device and protocol procedure related adverse events at Week 12 and at Week 24.

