7.5.2 Visits 1.2 and 2.2

Four and eight weeks after Visit 3, that is at week 16 and week 20 from Baseline Visit patients who decided to switch will take part in a virtual remote visit (Visit 1.2 and Visit 2.2 respectively).

Patients will be asked to fill in the following questionnaires:

- PDSS-2
- Pain VAS
- Parkinson Disease Questionnaire, Short Form (PDQ-8).
- 7.5.3 Visit 4

Twelve weeks after Visit 3, that is, at the end of the 12-week Long Term Intervention Period, all patients will participate in an in-clinic visit (Visit 4), where they will perform the same series of assessments as in the Baseline Visit and Visit 3. Patients will need to bring their FeetMe devices, their diaries, trackers and filled-in questionnaires to the visit.

The following assessments will be performed at Visit 4:

- Gait Assessments, which must be performed in the ON-phase:
 - 6 Minutes Walk Tests (6MWT)
 - Mini-BESTest.

During the 6MWT and the Mini-BESTest, patients must wear the insoles. Specific instructions set out in the Site User Manual must be followed when setting up and executing the assessments.

- Disease specific rating scales:
 - MDS-UPDRS
- Other Assessments:
 - FOG-Q
 - PDSS2
 - Pain VAS
 - PDQ39
 - Clinical Global Impression of Improvement / Patient Global Impression of Improvement (CGI/PGI-I)
- Potential adverse events and change in concomitant medication since the last contact.

- The source documents must be collected from the patients and the diary and tracker transcribed into the database.
- At the end of the visit the patients will return home with their devices and proceed into the Remote Gait Monitoring 3 (Section 7.4.4).

7.5.4 Remote Gait Monitoring 3

At the end of Visit 4, all patients will take the FeetMe Insoles with them to their homes. All patients will again use the insoles remotely while performing their day-to-day activities (including physiotherapy) for two weeks. Data will be recorded in standalone mode.

Once the Remote Gait Monitoring 3 period is completed, all patients will return all the FeetMe devices to the site via courier. The site personnel will make sure the data is downloaded as described in the Site User Manual.

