8.6.8 Clinical Global Impression of Improvement (CGI-I)

The Clinical Global Impression of Improvement is a standard clinician rating scale commonly used in Parkinsonism clinical trials, designed to assess the patient's improvement over a period of time (Guy, 1976). The CGI-I consists of a single assessment, scored on a scale ranging from 1 (very much improved) to 7 (very much worse). The investigator performs a medical examination and the scoring. The CGI-I takes around three minutes to complete.

The CGI-I will be performed at Visit 3 and Visit 4 (Appendix R).

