8.6.9 Patient Global Impression of Improvement (PGI-I)

The Patient Global Impression of Improvement is a standard patient self-rated scale, designed to evaluate the improvement of the patient's condition over a defined period of time from his/her own perception (Yalcin and Bump, 2003). The PGI-I consists of a single assessment, scored on a scale ranging from 1 (normal/least severe symptoms) to 4 (most severe symptoms). This assessment is self-administered by the patient. The PGI-I takes approximately three minutes to complete.

The PGI-I will be performed at Visit 3 and Visit 4 (Appendix Q).

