14.18.2 Clinical global impression of improvement

A compléter à Visite 3 et Visite 4 si applicable.

Veuillez mettre une croix en face de la réponse qui décrit le mieux l'évolution de l'état de santé du patient depuis sa dernière visite :

- Beaucoup mieux
- Mieux
- Pas de changement
- Un peu moins bien
- \circ Moins bien
- Beaucoup moins bien

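### The PGI-I and CGI-I forms ask about change since an undefined last visit, so the period rated is ambiguous, and change from Baseline to Week 24 is never asked

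*Protocol*

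**What the plan says.** Both improvement scales are rated twice: "The PGI-I will be performed at Visit 3 and Visit 4 (Appendix Q") and "The CGI-I will be performed at Visit 3 and Visit 4 (Appendix R"). The patient form asks for the answer that best "décrit le mieux l'évolution de votre état de santé depuis votre dernière visite" (Section 14.17.2). The clinician form asks for the one that best "décrit le mieux l'évolution de l'état de santé du patient depuis sa dernière visite" (Section 14.18.2).

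The exploratory endpoints in the Synopsis and in Table 5.1 place these scales under change from Baseline to Week 12, from Baseline to Week 24, and from Week 12 to Week 24. Sections 8.6.8 and 8.6.9 refer to improvement over a period but name no start point.

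Between the in-clinic assessments the protocol schedules contacts that it also calls visits. In the first 12 weeks every patient has "two remote visits: Visit 1 (four weeks after BL) and Visit 2 (eight weeks after BL"). In the second 12 weeks, at Weeks 16 and 20, only "patients who decided to switch will take part in a virtual remote visit" (Section 7.5.2).

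**The concern.** An improvement scale has no Baseline value to subtract. The rating is itself the change, and the anchor printed on the form alone determines which period it describes. If the anchor is unclear, the endpoint is unclear, and no analysis plan can recover a period that was never asked about.

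No other per-patient item fills the gap. Table 6.1 schedules the two global severity scales (CGI-S, PGI-S) at Baseline only, so change in global severity cannot be derived from them. The investigator questionnaire in Appendix E does ask about overall improvement and how the arms compare, but for patients as a group and at the end of the study. What is at stake is whether the per-patient global ratings at Weeks 12 and 24 can be read against the periods the endpoint list gives them.

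**Working it through.** No sample size, power or alpha figure is involved. The check sets the form wording against the visit schedule.

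**Inputs.** Baseline is Week 0, Visit 2 Week 8, Visit 3 Week 12, Visit 2.2 Week 20 (switchers only) and Visit 4 Week 24 (Table 6.1, Sections 7.4 and 7.5). Each visit after Baseline has a window of plus or minus 7 days counted from the original schedule; Baseline has none.

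**Formula.** Recall window = scheduled week of the rating visit minus scheduled week of the preceding visit. The range adds 1 week in each direction for each of the two visits that has a window.

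| Rated at | Patients | Remote visits counted | In-clinic visits only |
|---|---|---|---|
| Visit 3 | All | 12 − 8 = 4 weeks (2 to 6) | 12 − 0 = 12 weeks (11 to 13) |
| Visit 4 | Continued or stopped | 24 − 12 = 12 weeks (10 to 14) | 24 − 12 = 12 weeks (10 to 14) |
| Visit 4 | Switched | 24 − 20 = 4 weeks (2 to 6) | 24 − 12 = 12 weeks (10 to 14) |

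**Against the listed periods.**

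- Baseline to Week 12: covered on the in-clinic reading, not on the literal one. There the window is 4/12, one third of the period.
- Week 12 to Week 24: covered for everyone on the in-clinic reading; on the literal reading, only for patients who continued or stopped.
- Baseline to Week 24 (24 − 0 = 24 weeks): covered on neither reading.

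**Which reading does the protocol support?** Its own use of the word is mixed. The headers of the pain VAS (Appendix H) and the PDSS-2 (Appendix P) call for completion at every visit and include the remote ones. The header of the freezing of gait questionnaire (Appendix O) also says every visit but lists only Baseline, Visit 3 and Visit 4. Section 8.6.8 has the investigator examine the patient before scoring the CGI-I, and no examination is listed at the remote visits in Sections 7.4.2 and 7.5.2. That favours the in-clinic reading for the clinician. For a patient who completed questionnaires for Visit 2 at Week 8, the literal reading is natural. Nothing in the protocol settles the matter.

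**The case against.** The strongest reply is that the last visit obviously means the last in-clinic visit. At the remote contacts patients only complete PDSS-2, pain VAS and PDQ-8, and nobody examines them. On that reading two of the three listed periods are measured, every patient has the same 12-week window, and the switcher difference disappears. This is a fair reading, and for the CGI-I probably the likelier one. It does not close the point: the protocol does not state it, the PGI-I is answered by patients who may read it otherwise, and Baseline to Week 24 remains unasked.

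A reader might go further and infer three things that the documents do not support.

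- That the Week 12 rating definitely leaves out the first 8 weeks, so that a patient who improved early and then held steady is necessarily scored as unchanged. This follows only if remote visits count. The same holds for the inference that only one third of the 12-week change is captured, which also assumes linear improvement.
- That the Week 24 results compare a 4-week window with a 12-week one. Section 9.5.3 plans no comparison of switchers with other patients. Long-term efficacy compares the arms among patients who continue, none of whom has Visits 1.2 and 2.2; patients who stop are a separate objective; switchers are described on their own. Even read literally, a switcher's window is 4 weeks at both Visit 3 and Visit 4.
- That the anchor favours one arm. All patients have Visits 1 and 2, so the scheduled Visit 3 anchor is the same in both arms.

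**Conclusion.** The point stands as a mismatch between form and endpoint. The anchor is undefined, the window it implies is 4 or 12 weeks depending on the reading, and individual answers may mix the two with no means of separating them later. Baseline to Week 24 is listed for these scales but measured under neither reading; that part needs no assumption about how the wording is understood.

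The 4-week figures rest on counting remote visits as visits, and the 12-week figure at Visit 3 on not counting them. The documents do not decide between these, so neither should be reported as the settled window.

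The consequence is limited. These are exploratory endpoints summarised descriptively (Sections 9.2.6 and 9.5.3), and no hypothesis in Section 9.2.2 depends on them. The correction should be made because it is cheap and the lost information cannot be recovered afterwards, not because the trial's main conclusion is at risk.

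**What to change.** 1. On both forms, replace the reference to the last visit with a named anchor, identical for all patients: *depuis la visite Baseline* at Visit 3 and *depuis la Visite 3* at Visit 4.
2. For Baseline to Week 24, choose one: add a second line at Visit 4 reading *depuis la visite Baseline*, or delete that period for CGI-I/PGI-I from the Synopsis and Table 5.1. Deletion is reasonable if 24-week recall is judged unsuitable.
3. In the endpoint lists, report the rating itself at each visit over its named anchor, not a change in the rating.

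The cost is a few words on two one-item forms, at most one extra tick per form at Visit 4, and an edit to the endpoint lists. Under Section 12.1, revised study material must be re-submitted to the ethics committee; notification alone would not be enough.
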